- Help clients schedule appointments at the Hope Center
- Clean and help organize study clinic

- Will perform home visits as necessary in coordination with the receptionist and study doctor
- Will help phone subjects for follow-up in coordination with the receptionist and study doctor
- Perform duties given by receptionist or study coordinator

Driver

- Transport specimens and data files
- Assist the administrator in purchase of supplies and equipment
- Maintain car and ensure it is running well and has fuel
- Perform duties given by administrator or principal investigator
- Pick supplies from the office to the clinic

Study Population & Recruitment

The study will be a prospective randomized clinical trial enrolling HIV-positive women who receive care at the Coptic Hope Center for Infectious Diseases in Nairobi, Kenya. The study clinic will screen at least 2,400 HIV-positive women from the Coptic Hope Center for cervical cancer and, of whom, approximately 400 will be enrolled and randomized to receive treatment.

It is estimated that at least 2,400 women will need to be screened in order to identify 400 women with high-grade intraepithelial lesions. This is based on a prospective analysis of 500 HIV-positive women who underwent Pap smear screening at the Hope Center between July and November 2009. In this analysis, 187 (37%) women had normal cytological results, 292 (59%) had abnormal cytological results, and 21 (4%) had results which were indeterminate due to inflammation, inadequate sample collection, or insufficient data. Abnormal cytological results included 77 women (15%) with atypical squamous cells of undetermined significance (ASCUS), 121 (24%) low-grade squamous intraepithelial lesions (LSIL), and 92 (18%) high-grade squamous intraepithelial lesions (HSIL).

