Interested women will be referred to the study clinic (Room A) which will be staffed by two study nurses trained to perform Pap smears on the same day after obtaining informed consent for screening. Women who enrolled in the screening portion of the study and obtained a Pap smear will be asked to return to the study clinic (Room A) for results 2 weeks later. If Pap result is positive for HSIL, the subject will be referred to a separate room (Room B) where a study doctor and a study nurse will obtain a biopsy to confirm CIN 2 and 3 by histology. From this point, the subject will return to Room B and see the study doctor and nurse for further follow-up. Four to six weeks after biopsy, the subject will return for her results and to discuss treatment options. At this point, study staff will obtain informed consent for randomization and follow-up, and the study doctor will randomize histology-confirmed subjects (approximately 400 women) to LEEP or cryotherapy. Criteria for being ineligible for cryotherapy include if a polyp or anatomic defect prevents access to the cervix and/or if the lesion size is >75% of the cervix or is larger than the cryoprobe tip, or if the lesion is not visible in its entire extent or extends more than 2 to 3 mm into the endocervical canal. If any of these subjects are diagnosed with severe cervical disease confirmed by

histology at these later screening time points, they will be offered LEEP by the study or referred for appropriate care.

Patients who require further care for cervical disease unavailable at the study clinic (eg. hysterectomy) or who decline to enroll in the treatment portion of the study will be referred to KNH. Through patient tracing the study doctor and staff connected to the KNH gynecology department will make best efforts to assure that patients receive proper care. Referral notes and copies of results for histopathology, cytopathology, CD4 count, and HIV viral load will be sent with the patient during referral. All study specific documentation including study numbers and title will be removed. Only the subject's name and age, as is relevant to the referral, will be on the documents sent for clinical care at KNH or Coptic Hospital. Subjects will receive government subsidized care at these sites but the study will not pay for these interventions or treatment.

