exited subject becomes eligible for re-enrollment due to re-reading of cytology results (See QA/QC section), then re-enrollment consenting will be done at the disclosure visit for the new results. All consenting study staff members will be able to describe study procedures in English, Kiswahili and possibly another local language. Other nursing and study staff are available and should be contacted in the case of a participant who presents for enrollment but is not conversant in any of the languages the consenting staff member speaks. Consent documents will be prepared in both English and Kiswahili at a basic reading level. The English version will be used by study staff to produce the Kiswahili version and several members of the staff will review the document to assure its accuracy and readability.

Participants will be encouraged to ask questions at any point during the consent process and will be given a copy of the document to review on their own. If a participant has a question that cannot be answered by the consenting staff member, other study staff will be available for consultation. The patient may also contact other study staff at her convenience. The participant may also interrupt the consent process at any time if she needs more time to consider her participation.

Subjects with initial Pap smear results that are Normal or ASC-US will be exited from the study after receiving their Pap smear results. Subjects with LSIL Pap smear results will be offered Colposcopy. According to the 2012 ASCCP guidelines, participants found with LSIL in the absence of HPV co-testing should be recommended colposcopic evaluation and biopsy. These biopsy histology results will be treated the same as other study histology, including possible treatment randomization for CIN 2/3 and CIS. This will enable researchers to monitor lesions which may escalate from low-grade to high-grade in subjects who may be eligible for subsequent randomization. Results from repeat Pap-smears will be treated the same as results from initial Pap smears: Women with Normal/ASC-US results will be exited from the study. Subjects with HSIL/ASC-H/HSIL-invasion-not-ruled-out and results

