suggestive of cervical carcinoma (i.e. high grade intra-epithelial lesions) will undergo colposcopy with biopsy, and may potentially be eligible for randomization upon confirmed histology results. If a subject with high grade intraepithelial lesions detected on study-related Pap smears is later found to have normal or ASCUS on a follow up Pap smear (study related or not) that occurs prior to or in lieu of a colposcopic evaluation, the subject will still be required to have a study related colposcopy and biopsy.

Subjects who have biopsy-confirmed CIN 2, 3 or CIS will be eligible for the randomization and treatment portion of the study. They will be presented with the consent information upon receipt of biopsy result. Subjects with biopsy results suggestive of cervical carcinoma will be exited from the study and referred for further evaluation and management at KNH. Subjects with CIN I biopsy results will be asked to return to the clinic for repeat Pap smear in 6 months and will remain in the study. If a subject receives three consecutive CIN I histology results, she will be offered LEEP treatment by the study doctor. These participants will be treated and followed the same as other non-randomized LEEP participants.

Of note: Women with normal or with ASCUS Pap smear results (that are exited from the study) will be referred for subsequent cervical screening follow-up at the Hope Center Cervical Cancer Screening Program (CCSP). This program is administered by the Coptic Hospital and is supported by the Coptic Mission, PEPFAR, and other donor funding. The CCSP offers free cervical cancer screening to HIV-positive women enrolled in the Coptic Hope Clinic. Currently, a single visit ‘screen-and-treat’ strategy for cervical cancer prevention and treatment will be used. The screen-and-treat method involves visual inspection of the cervix followed by treatment of precancerous lesions by cryotherapy at the same visit. Patients who cannot be treated with cryotherapy are referred to KNH for subsidized cervical

care and treatment. As all study subjects are drawn from the Coptic Hope HIV clinic, they are all eligible to be screened, treated, and followed at the CCSP.

If a woman exited from her normal or ASCUS Pap smear result prefers to rescreen with the study, she may be re-enrolled using the re-enrollment consent form.

Study Procedures

1. SCREENING visit (at least 2,400 patients) (see Study Flow Diagram I, Enrollment)

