5. Six, twelve, eighteen, and twenty-four months after randomization visits for RECURRENCE (approximately 400 patients) (see Study Flow II)

- After the 9-11-week visit, randomized participants and those who undergo LEEP but are not randomized because their lesions are not amenable to cryotherapy will return at 6, 12, 18, and 24 months after treatment is administered. At the 24 month visit, the subject will be exited from the study. At these 6-month interval visits, the following will be performed in order:
 - Pap smear to detect recurrence of cervical intraepithelial lesions
 - Same Pap smear swab will be used to assess the presence of Human Papillomavirus (HPV)
 - Blood (5 mls) will be drawn to check for CD4 count
 - “Pap Smear” questionnaire completed
- Pap smear results that are normal, ASCUS, will be filed in the participants file and disclosed at the next scheduled follow-up visit. If pre-cancerous lesions by cytology have recurred then patient will be contacted to return to the study clinic to undergo colposcopic directed biopsy prior to treatment. Results of the colposcopic examination will be entered in the “Colposcopy” questionnaire..
 - If histology-confirmed lesions can be treated by LEEP, then the patient will receive a free LEEP and “Treatment” questionnaire will be filled.
 - If histology-confirmed lesions are too large or cancerous for LEEP then patient will be referred to KNH for subsidized care at this government

hospital. The study will not pay for this treatment. Patients will be given follow-up appointments in the study clinic after referral to determine outcomes.

- Phone calls and home visits will be performed sequentially in the case of a subject who has been lost to follow-up (LTFU) after screening or randomization (see LTFU section). LTFU will be prepared and discussed at weekly clinic meetings. Written reports will be prepared from these meetings and sent to co-investigators. Home visits will be performed by community health workers trained to be discreet in their approach to finding patients. They will not wear clothes that would identify them as health workers and will only use public transportation or unmarked private vehicles. They may ask about the participant's health or whereabouts.

6. Specimen transportation

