The sample size was calculated to detect a 10% difference in treatment outcomes between LEEP and cryotherapy (4% versus 14%)²⁶ with 80% power and a 0.05 significance level. Accounting for the possibility of a 20% loss-to-follow-up rate over two years, we estimated that 400 women with high grade lesions would need to be enrolled in the study with 200 women randomized to each arm. It is estimated that 200 women in each arm will allow detection of a 0.25 log₁₀ HIV virus level difference in cervical shedding between the two arms with greater than 90% power. Based on results from an ongoing cervical cancer screening study implemented at the Hope Center in 2009, our estimation of the prevalence of high-grade intraepithelial lesions is about 18%. Given this estimate and the number of women who are likely to be eligible for randomization, we calculate that we need to enroll 2,400 women for initial screening.

The primary analysis of the study will be to compare treatment outcomes between the LEEP and cryotherapy intervention arms in an intent-to-treat analysis. Treatment outcomes will be measured by Pap smears taken every 6 months during two-year follow-up. Pap smears demonstrating high-grade intraepithelial lesions will be considered positive and compared against negative or low-grade intraepithelial lesions. A Chi-square test will be used to compare the percentage of positive Pap smears between the intervention arms at 6, 12, 18, and 24 months. Secondary analyses will compare cervical HIV-1 RNA viral shedding between the treatment arms. A comparison of the average area under the curve (AAUCMB) of long-transformed HIV-1 RNA cervical viral loads will be performed between the two arms using an analysis of covariance (ANCOVA) model.

Our analysis will include contraceptive history as a potential confounder. While there has been some suggestion in the literature that HIV infectivity among women on oral

contraceptives is increased,^{33, 34} a recent study from the UW did not show a significant increase in levels of HIV RNA in cervical samples obtained from women on hormonal contraception.³⁵ A more recent multicenter randomized controlled trial performed in Asia and Africa also did not find an association between hormonal contraceptive use and increased HIV transmission.³⁶ However, increased viral shedding due to hormonal contraceptive use remains an important and interesting question and one that we will examine in our study.

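### Women can be randomised on an LSIL smear with a CIN 2/3 biopsy, but recurrence is scored by smear alone with LSIL on the negative side, so biopsy-proven recurrences after an LSIL smear are not counted

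*Combined protocol and SAP*

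**What the plan says.** **Entry.** Study Population & Recruitment states: "Subjects with LSIL Pap smear results will be offered Colposcopy". It continues: "These biopsy histology results will be treated the same as other study histology, including possible treatment randomization for CIN 2/3 and CIS". Eligibility then rests on histology, with no condition on smear grade: "Subjects who have biopsy-confirmed CIN 2, 3 or CIS will be eligible for the randomization and treatment portion of the study". Study Procedures item 2 repeats the offer of colposcopy after LSIL.

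**Outcome.** Statistical Methods states: "Treatment outcomes will be measured by Pap smears taken every 6 months during two-year follow-up". The scoring rule is: "Pap smears demonstrating high-grade intraepithelial lesions will be considered positive and compared against negative or low-grade intraepithelial lesions". A chi-square test compares the percentage of positive smears at 6, 12, 18 and 24 months. There is no exception for women who entered on LSIL, and biopsy results play no part.

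**Follow-up biopsy.** Study Procedures item 5 files normal and ASCUS smears. For other results it says: "If pre-cancerous lesions by cytology have recurred then patient will be contacted to return to the study clinic to undergo colposcopic directed biopsy". Histology-confirmed lesions treatable by LEEP are then retreated.

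**Competing text.** Interim Efficacy Analyses gives the primary outcome as recurrence of CIN grade 2 or 3, with no ascertainment rule. On entry, an earlier paragraph of Study Population & Recruitment sends only HSIL smears to biopsy. The histology paragraph of Notification of Results lists only high-grade or cancer results as needing biopsy. The tracing section for non-randomised women still refers to a six-month repeat smear after LSIL.

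**The concern.** A woman who enters by the LSIL route has CIN 2/3 or CIS that showed on cytology as low-grade. If the lesion persists or returns and again reads LSIL, the scoring rule classes her as not recurred. Take a possible record: screening smear LSIL, biopsy CIN 3, cryotherapy, month-6 smear LSIL, follow-up biopsy CIN 3, LEEP, then normal smears. The study would have found and retreated a treatment failure, yet under Statistical Methods she never has a positive outcome.

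At stake are the reported recurrence rates and the absolute difference between arms. Objective 1 concerns recurrence of CIN, and the Background justifies using both cytology and histology because CIN recurrence is the outcome. The scoring rule uses only the first.

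**Working it through.** **1. The plan's own sample size.** Inputs from Statistical Methods: 4% v 14%, 80% power, significance level 0.05 (two-sided assumed), 20% loss. The pooled-variance formula gives 128 evaluable per arm, and 128/0.8 = 160 enrolled. The stated 200 per arm is not reproduced; it is larger than these inputs need. That is a separate matter, but it leaves slack: 200 x 0.8 = 160 evaluable per arm. Power is Φ{[d - 1.96√(2p̄(1-p̄)/n)] / √[(p1(1-p1)+p2(1-p2))/n]}. With d = 0.10, p̄ = 0.09 and n = 160 this is Φ[(0.1000 - 0.0627)/0.0315] = Φ(1.18) = 88%.

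**2. How many women enter by the LSIL route.** The documents give two incompatible counts.
- Pilot of 500 women (Study Population & Recruitment): LSIL 2,400 x 121/500 = 581; HSIL 2,400 x 92/500 = 442.
- Study Procedures item 2: 2,400 - 1,700 = 700 not in the no-biopsy group, of whom about 400 are high-grade, leaving about 300.

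Biopsy yields are not given. Assume CIN 2+ in a = 10-25% of LSIL and b = 50-80% of high-grade smears, with every woman accepting colposcopy. LSIL-route share f = La/(La + Hb).
- Pilot counts: 58.1/(58.1 + 353.6) = 14%, up to 145.25/(145.25 + 221) = 40%.
- Item 2 counts: 30/(30 + 353.6) = 8% (with H = 442; 9% with H = 400), up to 75/(75 + 200) = 27% (with H = 400).

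**3. Effect on rates and power.** Let q be the chance that a recurrence in an LSIL-route woman gives a high-grade smear (assumed 0.15-0.40), and suppose smears detect every recurrence in the others. Both arm rates are multiplied by k = 1 - f(1 - q). At n = 160 per arm:

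| f | q | k | LEEP v cryotherapy | Power |
|---|---|---|---|---|
| 0 | - | 1 | 4.00% v 14.00% | 88% |
| 0.18 | 0.40 | 0.892 | 3.57% v 12.49% | 84% |
| 0.18 | 0.15 | 0.847 | 3.39% v 11.86% | 82% |
| 0.30 | 0.40 | 0.820 | 3.28% v 11.48% | 80% |
| 0.30 | 0.15 | 0.745 | 2.98% v 10.43% | 76% |

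With the item 2 shares (f = 0.08 to 0.27) the same formula gives 78-86%. The factor k cancels from the risk ratio; only the absolute rates, their difference and power change.

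**The case against.** **The interim section may already define a histological endpoint.** If recurrence of CIN 2 or 3 there means histology, the woman in the example is counted. But the section does not say how recurrence is ascertained, and the Colposcopy form labels smear categories as LSIL (CIN 1) and HSIL (CIN 2 & 3), so a cytological reading is equally open. If histology is meant, the interim and final analyses use different endpoints and Statistical Methods still has to change.

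**The LSIL route is not consistently described.** This is true: three places conflict with the explicit text and must be reconciled. Colposcopy is also only offered, so full uptake is generous.

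**The size rests on assumptions.** This also stands. Neither q nor the biopsy yields come from the documents, and nothing shows that a recurrence keeps its entry smear grade. The power figures also give high-grade-route women perfect smear detection. If detection there were 0.75, rates would be 3.0% v 10.5% and power 76% with no LSIL entrants at all. That loss belongs to smear sensitivity in general, not to this mismatch.

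**Stronger readings a reader might infer.** One is that unchanged disease always counts as cure in these women. It does not: a later high-grade smear still counts. Another is that the rule favours one arm or could create a false difference. The rule is identical in both arms and entry smear is balanced in expectation by randomisation. A third is that the trial is underpowered. Three of the four scenarios in the table still reach 80%.

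**Conclusion.** The mismatch is in the text and should be corrected. LSIL-route women meet the smear definition of non-recurrence at entry, and CIN 2/3 confirmed by follow-up biopsy after an LSIL smear is left out of the outcome. The consequence is understated recurrence in both arms, a smaller absolute difference and some loss of power.

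The size cannot be fixed from the documents. The 76-84% power range, against 88%, holds for LSIL-route shares of 18-30%, q of 0.15-0.40 and perfect detection in the remaining women. The lower set of counts (8-27%) allows a smaller effect. Whether a follow-up LSIL smear always leads to biopsy is also not expressly stated. Item 5 files only normal and ASCUS results, so LSIL appears to fall in the recall group.

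**What to change.** In Statistical Methods, define recurrence as a high-grade follow-up smear, or follow-up histology (colposcopic biopsy, endocervical curettage or retreatment LEEP specimen) showing CIN 2, CIN 3, CIS or invasive carcinoma, whatever smear grade prompted it. Exclude explicitly the baseline biopsy and the index LEEP specimen. Study Procedures item 3 sends the index LEEP piece for histology, so without the exclusion LEEP-arm women could be scored as recurring on the day of treatment.

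Compare arms on cumulative recurrence by each visit through 24 months, since a per-visit percentage of positive smears does not match this definition. Use the same definition in Interim Efficacy Analyses. Report results by entry smear (LSIL v high-grade) as a descriptive breakdown. Reconcile the passages that disagree on the LSIL route.

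The cost is a rewritten endpoint definition and comparison, and variables derived from the Cytology and Histology Reports already collected; no new procedure is needed. The downsides are that the endpoint mixes smear and biopsy, gains histology only in women biopsied under item 5, and is ascertained by unblinded staff. Biopsy uptake after an abnormal smear should therefore be reported by arm. The change should be made before comparative data are reviewed.

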The recent scale-up of antiretroviral treatment programs in resource-limited settings provides an unprecedented opportunity to implement a comprehensive cervical cancer screening and treatment program for women who, by virtue of having HIV, are at significant risk for cervical disease. Unfortunately, even if screening is offered free of charge to millions of women living with HIV, it is unclear which treatment modality for pre-cancerous cervical lesions will be most effective since HIV appears to affect outcomes of treatment by increasing the recurrence and severity of cervical disease. Cervical treatment may also increase shedding of HIV from the cervix which may put discordant couples at risk and possibly spread HIV more widely. This study proposes to randomize HIV-positive women with cervical intraepithelial neoplasia grade 2 and 3 (CIN 2 and 3) to cryotherapy vs. loop electrosurgical excision procedure (LEEP) and measure the recurrence of cervical disease in each group over 2-years of follow-up as well as HIV shedding from the cervix for 3 weeks after treatment.

Our hypothesis is that compared to cryotherapy, LEEP is significantly more likely to prevent recurrence of cervical lesions over 2 years of follow-up and less likely to cause shedding of HIV-1 from the cervix over 3 weeks of follow-up.

The objectives of this study are:

1. To compare the rate of recurrence of cervical intraepithelial neoplasia among HIV-positive women receiving cryotherapy versus LEEP over 2 years of follow-up
2. To compare the shedding of HIV-1 from the cervix between HIV-positive women receiving cryotherapy versus LEEP over 3 weeks of follow-up

Background

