There has been some controversy surrounding cervical treatment and whether or not it is associated with adverse pregnancy outcomes. Sadler et al. showed in their retrospective analysis of 652 women that had undergone LEEP, laser ablation or laser conization that LEEP did not increase the incidence of preterm delivery.²⁴ However, the authors did note a significant increase in premature rupture of membranes. Acharya et al., in their matched cohort of 428 women undergoing LEEP, also found no correlation between the procedure and premature delivery or low birth weight, but they did find a significantly higher number of women with pregnancy complications, which included premature contractions, infections and cervical incompetence.²⁵

Finally, there is evidence that cryotherapy may be less effective compared to LEEP in preventing the recurrence of cervical intraepithelial neoplasia though the literature is equivocal. Overall, there have been few studies comparing the efficacy in treatment between cryotherapy and LEEP, especially in HIV-infected women. Chirenje et al. found a significant difference in the failure rate of cryotherapy versus LEEP, however his numbers were small with only 6 high-grade recurrences in the cryotherapy arm (14.3%) and 2 in the LEEP arm (4%).²⁶ Moreover, neither HIV nor HPV shedding was measured and follow-up time was only one year. In another randomized study comparing cryotherapy and LEEP, this time a larger study in non-HIV-infected women, no significant difference was found between the two arms in terms of failure, defined as either recurrence or persistence.²³ Additionally, in a 2000 Cochrane review, it was stated that “evidence suggests that there is no obviously superior surgical technique for treating cervical intra-epithelial neoplasia.”²⁷

If cryotherapy is found to result in a greater number of failures, it may require more frequent and careful follow-up screening than LEEP, and therefore may not be as cost-effective or therapeutic for the patient. As a result, the individual and public health risks of a “screen and treat” approach for cervical cancer screening and treatment among HIV-positive women may be much greater than its benefits.

Rationale

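### The primary analysis is four unadjusted visit-wise tests, with no deciding visit and no rule for scoring retreated women, so the 2-year recurrence comparison is not defined

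*Combined protocol and SAP*

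**What the plan says.** - **Objective.** "To compare the rate of recurrence of cervical intraepithelial neoplasia among HIV-positive women receiving cryotherapy versus LEEP over 2 years of follow-up".
- **Primary analysis (Statistical Methods).** An intention-to-treat comparison in which a high-grade smear is positive and anything lower is negative. A chi-square test is used to "compare the percentage of positive Pap smears between the intervention arms at 6, 12, 18, and 24 months".
- **Sample size (same section).** 4% v 14%, 80% power, significance level 0.05, 200 per arm, "Accounting for the possibility of a 20% loss-to-follow-up rate over two years". The time horizon of 4% v 14% is not given. Background says of the study cited for these rates that "follow-up time was only one year".
- **Follow-up (Study Procedures, item 5).** A woman with recurrence on cytology is recalled: "patient will be contacted to return to the study clinic to undergo colposcopic directed biopsy prior to treatment". Then: "If histology-confirmed lesions can be treated by LEEP, then the patient will receive a free LEEP". This applies in both arms. Smears are scheduled to month 24: "At the 24 month visit, the subject will be exited from the study".
- **Statistical considerations for LTFU.** Lost women contribute time and data while they remain in the study. The worked example refers to a survival analysis.
- **Study Stopping Criteria and Interim Efficacy Analyses.** The primary outcome is recurrence of CIN 2 or 3. O'Brien-Fleming boundaries with Lan-DeMets spending hold type I error at 0.05 over interim looks at about months 9, 15, 21 and 27.

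**The concern.** Statistical Methods is where the primary test should be fixed, and it fixes four. It does not say whether month 24 decides, whether any significant visit suffices, or whether all four must agree. Intention to treat settles which arm a woman belongs to. It does not settle what outcome she has at month 18 if she recurred at month 6 and had LEEP in between.

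That omission matters because retreatment is selective. If cryotherapy fails more often, more cryotherapy women receive LEEP during follow-up, and their later smears may then be negative. A real disadvantage of cryotherapy could be reported as no difference at month 24 because its failures were treated. If month 6 decides, later failures are ignored. If any visit counts, the false-positive rate usually exceeds 5%. One dataset could therefore support several primary results, in a trial whose investigators and staff are not blinded.

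**Working it through.** **Inputs from the document:** 4% v 14%, 200 per arm, 20% loss over two years, two-year follow-up, four visits, 0.05 level. **Assumed, because the document is silent:** two-sided test, loss of 5% per visit, timing of recurrence, share retreated, and smear positivity after retreatment (0–14%).

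**1. The plan's own sample size.** With mean proportion 0.09,

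n = [1.96·√(2·0.09·0.91) + 0.842·√(0.04·0.96 + 0.14·0.86)]² / 0.10² = (0.793 + 0.335)² / 0.01 ≈ 128 per arm.

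Then 128/0.8 = 160 per arm (184 with continuity correction). The stated 200 is not reproduced, but it is larger than one comparison needs. It would not cover four Bonferroni tests at 0.0125 each: 182 evaluable, or 182/0.8 ≈ 228 per arm.

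**2. If 4% v 14% holds at the visit tested.** Power at 190/180/170/160 women per arm (months 6/12/18/24) is 93/92/90/88%.

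**3. If 4% v 14% is the 24-month cumulative risk.** Take failures spread evenly over the four visits, all retreated and none positive afterwards. Month 24 then compares 1.0% with 3.5%:

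(0.025·√160 − 1.96·√(2·0.0225·0.9775)) / √(0.01·0.99 + 0.035·0.965) = −0.454, so power is 32%.

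Carrying failures forward restores 4% v 14% at 160 per arm:

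(0.10·√160 − 0.793)/0.3985 = 1.18, so power is 88%.

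Simulation (200 per arm, 25–90% of failures by month 6):

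| Analysis | Power |
|---|---|
| Month 6 alone | 36–92% |
| Month 24, all failures retreated | 0–44% |
| Month 24, 60–80% retreated, half of the rest positive | 10–55% |
| Month 24, 60% retreated, all the rest positive | 48–69% |
| First recurrence through month 24 | 91–94% |

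The 0% is an extreme: no failures after month 12 and none positive after retreatment. First recurrence exceeds 88% here because women who recur before being lost still count.

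**4. If 4% v 14% is the one-year risk and year 2 repeats it.** The cumulative risks are 1 − 0.96² = 7.8% and 1 − 0.86² = 26.0%. Month-24 power is 47–68% with all retreated and year-2 failures spread evenly. It is 88–92% with 60% retreated and all the rest positive. First recurrence has 99% or more.

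**5. Error across visits.** Four independent tests give 1 − 0.95⁴ = 18.5%. Simulated under no difference and scored by current smear, any-of-four gives 5–16% at 4% recurrence and 8–19% at 9–26%. It is lowest when failures come early and all are retreated. Carrying failures forward alone does not cure this: any-of-four is then still about 10.5–13% (160 per arm, null recurrence 9–30%).

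**6. False-positive smears.** If one high-grade smear counts as recurrence and a fraction f of smears is falsely positive, the ever-positive risk is 1 − (1 − p)(1 − f)⁴. At 160 per arm:

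| f (assumed) | LEEP v cryotherapy | Power, first recurrence | Power, month 24, even timing |
|---|---|---|---|
| 0 | 4.0% v 14.0% | 88% | 32% |
| 1% | 7.8% v 17.4% | 74% | 24% |
| 2% | 11.5% v 20.7% | 61% | 19% |
| 3% | 15.0% v 23.9% | 52% | 16% |

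**The case against.** **The intended analysis can be inferred.** The objective speaks of a rate over 2 years. The loss-to-follow-up text has women contributing time and mentions a survival analysis. The interim section refers to a single primary outcome with 80% power at the end of the study. Together these lean towards a cumulative or time-to-event reading, and under it most of the problem disappears. But the survival analysis appears only as an example within a rule for lost women, and the section that states the primary analysis specifies a different test. The lean makes the repair easy; it does not make it.

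**Type I error is already controlled.** It is, over interim looks. A reader might infer that the plan has no error control at all, which would be wrong. The gap is across the four visit-specific tests.

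**The endpoint is not contradictory.** A reader might infer a conflict between high-grade cytology in Statistical Methods and CIN 2 or 3 in the interim section. The document does not prove one. The Colposcopy form labels an HSIL smear as CIN 2 & 3, and the interim section never mentions biopsy. This is an ambiguity to settle.

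**The low power figures rest on assumptions.** That stands. Only confirmed lesions that LEEP can treat, in women who return, are retreated by the study, so all retreated is a limiting case.

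**False positives hurt the proposed endpoint too.** Also true, and power could fall below the planned 80%. The same false positives lower month-24 positivity further, to 16–24% with even timing, so they argue for choosing the endpoint with care and not for keeping the current analysis.

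**Conclusion.** The concern holds. As written, the primary analysis does not identify one comparison. Its missing scoring rule can decide whether a true 4% v 14% difference is usually found or usually missed.

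That finding is textual and needs no simulation. The sizes do need assumptions. With 4% v 14% as the 24-month cumulative risk and all failures retreated, month-24 positivity has about 0–44% power against about 91–94% for first recurrence. Any-of-four testing has about 5–19% type I error. The loss of power is smaller if fewer women are retreated or if the rates are one-year risks.

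Two stronger readings should be avoided. It is not shown that no visit could measure 2-year recurrence: month 24 would if earlier failures were carried forward. Nor is it shown that the trial is underpowered as enrolled: 200 per arm is ample for one 4% v 14% comparison. It must be fixed before analysis because it concerns the primary result.

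**What to change.** In Statistical Methods:

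1. Make the single primary analysis time to first recurrence over the four scheduled visits through month 24, by intention to treat. Censor women without recurrence at their last Pap, as the loss-to-follow-up section describes.
2. State that smears after study retreatment are not counted as new outcomes. State how treatment received elsewhere, already asked on the Follow-up Form, is handled.
3. Report the 24-month cumulative difference with a confidence interval. Make the visit-specific percentages descriptive.
4. Apply the interim boundaries to this one test.
5. Name one endpoint, high-grade Pap or biopsy CIN 2/3, and use it in Statistical Methods, the loss-to-follow-up section and Interim Efficacy Analyses. If biopsy is chosen, say how a positive Pap without a biopsy is scored.
6. State the horizon of 4% v 14% and restate power for the chosen endpoint: 88% at 160 evaluable per arm if it is the 24-month risk, or about 74/61/52% if one high-grade Pap counts and 1/2/3% of smears are falsely positive. Choose the endpoint before confirming the sample size.

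The cost is protocol and SAP wording plus a restated power figure. Visits, enrolment, forms and retreatment rules do not change. Recall for biopsy is already part of follow-up.
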